### 3. OBJECTIVES, ENDPOINTS, AND ESTIMANDS

Objectives	Endpoints

Primary:
 
 
To evaluate the safety and tolerability of multiple doses of PF-07081532, administered orally, in adult participants with inadequately controlled T2DM on metformin and, if enrolled, in non-diabetic participants with obesity.
 
	
Primary:
 
 
Assessment of AEs, safety laboratory tests, vital signs and 12-lead ECGs.
 

Secondary:
 
 
To characterize plasma PK of PF-07081532 following multiple doses administered orally, in adult participants with inadequately controlled T2DM on metformin and, if enrolled, in non-diabetic participants with obesity.
 
	
Secondary:
 
 
PF-07081532 plasma PK parameters AUC24, Cmax, Tmax on Day 1 and Day 42 and t1/2 on Day 42, as data permit.
 

Exploratory:
 
 
To characterize the PD effect on glucose, insulin, glucagon, and C-peptide excursions after a MMTT following multiple doses of PF-07081532, administered orally, in adult participants with inadequately controlled T2DM on metformin.
 
	
Exploratory:
 
 
CFB in response to MMTT at all postdose timepoints as specified in the SoA for AUC(0-4) for glucose, insulin, glucagon, and C-peptide.
 

 
To explore the PD effect on MDG*, HbA1c*, plasma glucose, plasma insulin, and HOMA-IR following multiple doses of PF-07081532, administered orally, in adult participants with T2DM inadequately controlled on metformin and, if enrolled, in non-diabetic participants with obesity.
 
	
 
CFB at all post-dose timepoints as specified in the SoA for:           
 
Fasting plasma glucose;
 
Fasting plasma insulin;
 
HOMA-IR;
 
HbA1c*;
 
MDG*.
 
 
 

Objectives	Endpoints


To assess the PD effect on body weight changes following multiple doses of PF-07081532, administered orally, in adult participants with T2DM inadequately controlled on metformin and, if enrolled, in non-diabetic participants with obesity.

	

CFB in body weight at all post-dose timepoints as specified in the SoA.

To further characterize plasma PK of PF-07081532 following multiple doses administered orally, in adult participants with inadequately controlled T2DM on metformin and, if enrolled, in non-diabetic participants with obesity.

	

Additional PF-07081532 plasma PK parameters following multiple dose administration including, as data permit: <math>AUC_{24}(\text{dn})</math>, <math>AUC_{\text{inf}}</math>, <math>AUC_{\text{last}}</math>, <math>C_{\text{av}}</math>, <math>CL/F</math>, <math>C_{\text{max}}(\text{dn})</math>, <math>C_{\text{min}}</math>, <math>R_{\text{ac}}</math>, <math>R_{\text{ac},C_{\text{max}}}</math>, <math>PTR</math>, <math>V_z/F</math>.

Estimands are not applicable.

\*not analyzed in non-diabetic population with obesity, if enrolled.

## 4. STUDY DESIGN

### 4.1. Overall Design

[figure not shown]
This is a randomized, double-blind (investigator- and participant- blind), sponsor-open, placebo-controlled, multiple oral dose-escalating study of PF-07081532.

In this study, adult participants with T2DM inadequately controlled on metformin will be enrolled and will receive PF-07081532 or placebo daily, for 42 days.

- Enrollment in 3 cohorts is planned with approximately 12 participants (9 PF-07081532: 3 placebo) per cohort.

A sample dosing scheme is provided below. Dosing in Cohort 1 will be conducted as shown. Increments in doses and duration of dosing at each step for subsequent cohorts, as well as the number of cohorts conducted, may be adjusted based on emerging data. The dosing scheme for each cohort will be provided in writing prior to its initiation.

**Figure 1. Sample Dosing Scheme**

If a participant does not tolerate dose increment to the next dose level, as determined by the investigator and with notification to the sponsor, the participant may be reverted to the previously tolerated dose level. Following this dose modification, 2 separate attempts at increasing the dose to the next dose level are permitted, per investigator discretion. If, per investigator assessment, unacceptable intolerance (eg, severe vomiting) occurs shortly following dose administration, the dose will not be re-administered on the same day, and the participant may resume dosing at the current dose level at the next scheduled dosing time. Participants whose dose level is tolerability-limited may continue in the study for the intended duration of their assigned cohort at their own individual MTD, as judged to be appropriate by the PI and sponsor.

The planned cohorts in the study (Cohorts 1-3) may be conducted concurrently, partially overlapping or sequentially. The sponsor may decide not to conduct all planned cohorts, if it is judged that study objectives have been met. Up to 3 additional cohorts may be enrolled if judged necessary to meet the study objectives. One or more of the study cohorts may be conducted in non-diabetic participants with obesity, see [Section 4.2.1](#) and [Section 5](#).

Determination of eligibility will occur within 28 days of randomization based on criteria including medical history, vital sign, ECG and laboratory parameters, as detailed in [Section 5](#). Participants deemed eligible will be admitted to the CRU 7 days prior to start of dosing (Day -7) and will remain on-site until at least Day 45, post first dose.

The treatment period with double-blind study intervention will be 42 days, with study drug administered once daily. The participants within a given cohort will be blinded to the study treatment (PF-07081532 versus placebo). Participants who discontinue prior to completion of the study may be replaced, at the discretion of the PI and sponsor.

Upon discharge from the CRU, participants will return to the CRU 7 to 14 days after the last administration of IP for an on-site follow-up visit. A further follow-up contact with participants will be conducted at least 28 days and up to 35 days after the last administration of IP; this contact may be done via a phone call.

The total duration of the study from the Screening visit to the last follow-up visit will be approximately 16 weeks of which 52 days will be inpatient at the CRU, followed by a follow-up period of 4-5 weeks, post last dose.

The study will be conducted in the USA.

## 4.2. Scientific Rationale for Study Design

The primary objective of the study is to evaluate the safety and tolerability of multiple doses of PF-07081532 administered with different doses and dosing schemes over 42 days in participants with T2DM, inadequately controlled on metformin. Due to the gastrointestinal-related tolerability issues associated with GLP-1 receptor agonism^12 that have been shown to tolerate with repeated dosing, this study will evaluate safety and tolerability of different starting doses and titration increments in order to optimize the titration schemes for studies of longer duration.

### 4.2.1. Population(s)

Participants enrolled in this study will be adults with inadequately controlled T2DM (as indicated by HbA1c at screening) on metformin monotherapy, which is considered first-line therapy for glycemic control according to current treatment guidelines. At screening, this study requires that participants with T2DM have been taking a minimum stable metformin dose of at least 500 mg/day for at least 2 months prior to the screening visit. The dose of metformin, where possible, is expected to remain the same until completion of study participation (ie, follow-up visit). Available in vitro data suggest that PF-07081532 is not expected to impact the PK of metformin via inhibition of OCT2, and the risk of a clinical interaction is deemed negligible. One or more cohorts of non-diabetic participants with obesity may be enrolled in this study. The safety, tolerability, PK and PD data collected in this study may be used to select doses and dosing scheme algorithms for future studies of PF-07081532.

The population planned for this study will be male and female adult participants. Female participants will be WONCBP, since at the present time embryofetal development toxicity studies with PF-07081532 have not been conducted. In male participants appropriate measures are expected to be followed to limit potential transfer of PF-07081532 in semen to partners (see [Appendix 4](#)).

### 4.2.2. Concomitant Medications

CCI [REDACTED]

[REDACTED] For more information regarding concomitant medications in this study, see [Section 6.8](#).

### 4.2.3. Study Blinding

To permit an unbiased assessment of safety, the participants' treatment assignments (PF-07081532 versus placebo, but not cohort designation) will be blind to both site staff (except those involved in preparation of doses) as well as the study participants. However, to permit real-time review of the safety and PK data, a limited number of sponsor study team members will be unblinded (see [Section 9.4](#)).

### 4.2.4. Endpoints

Clinical safety laboratory tests, thorough assessments of vital signs and 12-lead ECGs, physical examinations, and AE monitoring will provide essential data to evaluate the safety and tolerability of PF-07081532. To supplement standard clinical safety laboratory tests, calcitonin, amylase, lipase, TSH, T4 and lipid panel will be assessed based on the study population and guided by data available on marketed GLP-1R agonists. In addition, TBA will be assessed, based on non-adverse findings in the nonclinical studies with PF-07081532 (see [Section 2.2.2](#) and the IB).

While GLP-1R agonists typically are not associated with hypoglycemia unless co-administered with anti-diabetic agents that can cause hypoglycemia (such as insulin or sulfonylureas), blood glucose concentrations will be monitored throughout the study via a glucometer at least once daily (pre-breakfast), and careful monitoring of symptomatic hypoglycemic AEs will be performed.

In an effort to reduce variability and better quantify any potential changes in heart rate and BP during the study, all measurements of ECG and vital signs (pulse and BP) will be collected in triplicate (except as noted in the [SoA](#)) and the mean values will be used for analysis at each time point.

The effect of PF-07081532 on glucose response in participants with T2DM will be evaluated by determining the change from baseline in MDG. Since MDG is the time-averaged response over a day, it is expected that this glycemic parameter will be predictive of longer term glycemic control. The effect of PF-07081532 on body weight, FPG and other glycemic markers including insulin, C-peptide, HbA1c, and glucagon will also be assessed. FPG and FPI levels will be assessed and used to calculate HOMA-IR. In order to reduce variability in FPI for HOMA-IR calculation, triplicate measurements will be collected as indicated in the [SoA](#) and [Section 8.9.2](#). In an effort to reduce variability, minimize any potential effect of placebo or CRU confinement and better quantify any potential changes to these parameters, the participants will be admitted to the CRU on Day -7 in order to monitor compliance with background metformin and recommended diet.

Baseline (Day -1) assessments with time-matched procedures will permit within participant comparisons, as appropriate. In addition, placebo-adjusted (between participant) comparisons of dose-response will also be conducted.

#### **4.2.5. Collection of Retained Research Samples**

Retained Research Samples will be collected and stored for further analyses which may, for example, provide understanding of the study intervention.

#### **4.3. Justification for Dose**

Doses for the study will be determined considering all relevant information obtained from nonclinical safety studies along with safety, tolerability, and PK data observed in completed study C3991001, ongoing Study C3991002 and emerging data from prior cohorts of this study, as applicable. The dose levels to be assessed in this study are anticipated to be within the dose range evaluated in C3991002 (10 mg to 180 mg QD), where no safety concerns with PF-07081532 have been identified. The total duration of dosing for PF-07081532 or placebo in this study will be 42 days, as supported by completed nonclinical toxicity studies (see [Section 2.2.1.3](#)).

Cohort 1 will receive PF-07081532 20 mg, or placebo, QD for 28 days followed by 60 mg or placebo, QD for the remaining 14 days. This was selected to assess whether a starting dose of 20 mg QD offers a profile that will allow its use as the initial titration step in future longer duration studies. The dosing schemes in subsequent cohorts may be adjusted based on emerging data in order to generate valuable information (eg, on different starting doses or dose increment steps) that will enable optimization of the dosing schemes for use in future studies. The doses and dose increments will be selected for this study in order to obtain data on these initial steps and not to necessarily reach the target doses where efficacy of PF-07081532 could be evaluated in future studies of longer duration.

#### **4.4. End of Study Definition**

The end of the study is defined as the date of the last visit of the last participant in the study or last scheduled procedure shown in the [SoA](#) for the last participant in the trial globally.

A participant is considered to have completed the study if he/she has completed all periods of the study, including the last visit or the last scheduled procedure shown in the [SoA](#).

### **5. STUDY POPULATION**

This study can fulfill its objectives only if appropriate participants are enrolled. The following eligibility criteria are designed to select participants for whom participation in the study is considered appropriate. All relevant medical and nonmedical conditions should be taken into consideration when deciding whether a particular participant is suitable for this protocol.

Prospective approval of protocol deviations to recruitment and enrollment criteria, also known as protocol waivers or exemptions, is not permitted.

#### **5.1. Inclusion Criteria**

Participants are eligible to be included in the study only if all of the following criteria apply:

### Age and Sex:

1. Male and female participants must be between the ages of 18 and 70 years, inclusive, at the time of signing the ICD.
2. Females must be of non childbearing potential.
  - Refer to [Appendix 4](#) for reproductive criteria for males ([Section 10.4.1](#)) and females ([Section 10.4.2](#)) participants.

### Type of Participant and Disease Characteristics:

3. Patients with T2DM who are treated with metformin.

**Note:** Participants must be taking metformin monotherapy as their only anti-hyperglycemic treatment. Metformin dose must be at least 500 mg per day and must be stable, defined as no change in the treatment and participant-reported compliance with treatment, for at least 2 months prior to the screening visit.

4. HbA1c  $\geq 7.0\%$  and  $\leq 10.5\%$  at screening (confirmed by a single repeat, if necessary).

**Note:** For non-diabetic participants with obesity (if enrolled), HbA1c  $< 6.5\%$  at screening.

5. Participants who are willing and able to comply with all scheduled visits, treatment plan, laboratory tests, lifestyle considerations, and other study procedures.

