### Weight and BMI:

6. Total body weight  $> 50$  kg (110 lbs) and BMI  $\geq 24.5$  to  $\leq 45.5$  kg/m^2.

**Note:** For non-diabetic participants with obesity (if enrolled) BMI  $> 30.5$  to  $\leq 45.5$  kg/m^2.

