### Medical Conditions:

1. Evidence or history of clinically significant hematological, renal, endocrine, pulmonary, gastrointestinal, hepatic, psychiatric, neurological, dermatological, or

- allergic disease (including drug allergies but excluding untreated, asymptomatic, seasonal allergies at the time of dosing).
- Participants who have chronic conditions other than T2DM and obesity (for example, hypercholesterolemia or hypertension) but are controlled by either diet or stable doses of 2 or fewer medications may be included (for example, a participant with hypercholesterolemia on appropriate treatment is eligible). See [Section 6.8](#) for further information on concomitant medications.
  - For non-diabetic participants with obesity (if enrolled), a medical history of T2DM.
2. Diagnosis of type 1 diabetes mellitus or secondary forms of diabetes.
  3. Evidence or history of clinically significant cardiovascular disease. In particular, history of myocardial infarction, unstable angina, arterial revascularization, stroke, New York Heart Association Functional Class II-IV heart failure, or transient ischemic attack within 6 months of screening.
  4. Any malignancy not considered cured (except basal cell carcinoma and squamous cell carcinoma of the skin); a participant is considered cured if there has been no evidence of cancer recurrence in the previous 5 years.
  5. Acute pancreatitis or history of chronic pancreatitis.
  6. Acute gallbladder disease.
  7. Any condition possibly affecting drug absorption (eg, prior bariatric surgery, gastrectomy, or any area of intestinal resection, active inflammatory bowel disease or pancreatic insufficiency).
  8. Personal or family history of MTC or MEN2, or participants with suspected MTC per the investigator's judgement.
  9. Other medical or psychiatric condition including recent (within the past year) or active suicidal ideation/behavior or laboratory abnormality that may increase the risk of study participation or, in the investigator's judgment, make the participant inappropriate for the study.

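### Inclusion criterion 3 lacks the obesity-cohort note that criteria 4 and 6 carry, so read literally nobody could be eligible for an optional obesity cohort

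*Protocol*

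**What the plan says.** Protocol Section 5.1 opens with the rule "Participants are eligible to be included in the study only if all of the following criteria apply". Criterion 3 is "Patients with T2DM who are treated with metformin". Its note says "Participants must be taking metformin monotherapy as their only anti-hyperglycemic treatment" and adds a minimum dose and a stability period. Neither the criterion nor the note names a cohort or population.

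The next eligibility limits are handled differently. Criterion 4 (HbA1c) has a note beginning "For non-diabetic participants with obesity (if enrolled), HbA1c" and criterion 6 (weight and BMI) has one beginning "For non-diabetic participants with obesity (if enrolled) BMI". Each gives the obesity population its own limit.

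In Section 5.2, a sub-bullet of exclusion criterion 1 reads "For non-diabetic participants with obesity (if enrolled), a medical history of T2DM". Section 5 states that prospective approval of deviations from enrollment criteria, "also known as protocol waivers or exemptions, is not permitted", and Section 8 repeats the ban.

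The design nevertheless provides for the obesity population. Section 4.1 says "One or more of the study cohorts may be conducted in non-diabetic participants with obesity, see", followed by references to Sections 4.2.1 and 5. The primary and secondary objectives in Section 3 include this population on an if-enrolled basis.

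**The concern.** Two parts of Section 5 ask for opposite things of the same person. Criterion 3 requires T2DM treated with metformin; the exclusion sub-bullet requires an obesity participant to have no history of T2DM. The notes under criteria 4 and 6 show how the authors mark an obesity exception, and criterion 3 has no such mark.

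At stake is the optional obesity part of the study. A site that applies the text word for word would screen-fail every candidate. Section 5.4 does not allow people who fail eligibility to be rescreened, apart from COVID-19 and vaccination reasons. A site that applies the evident intent would enroll people who do not meet a numbered inclusion criterion, with no approved waiver to rely on.

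**Working it through.** The plan states no figure for this point, so the check is one of logic. A person is eligible if every inclusion criterion is met and no exclusion criterion is met.

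**Inputs**

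| Item | Source | Content | Obesity exception stated? |
|---|---|---|---|
| Joining rule | Protocol 5.1 | All inclusion criteria must be met | n/a |
| Criterion 3 and note | Protocol 5.1 | T2DM, on metformin monotherapy, stable for at least 2 months | No |
| Criterion 4 | Protocol 5.1 | HbA1c 7.0% to 10.5% | Yes: below 6.5% |
| Criterion 6 | Protocol 5.1 | BMI 24.5 to 45.5 kg/m² | Yes: above 30.5, up to 45.5 kg/m² |
| Exclusion 1, sub-bullet | Protocol 5.2 | No history of T2DM in obesity participants | Applies only to them |
| Waivers | Protocol 5 and 8 | Not allowed | No |

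**Candidates for an obesity cohort**

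1. *A person with obesity and no T2DM.* Criteria 4 and 6 can be met through their notes, and the exclusion sub-bullet is not triggered. Criterion 3 is not met, so the all-criteria rule makes the person ineligible.
2. *A person with obesity and T2DM on metformin.* Criterion 3 is met. At least 2 months of stable metformin treatment for T2DM is itself a history of T2DM, so the exclusion sub-bullet applies and the person is ineligible for an obesity cohort.
3. *Any other candidate* either lacks T2DM or has T2DM without metformin. In both cases criterion 3 is not met.

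The literal eligible set for an obesity cohort is therefore empty. Criteria 4 and 6 do not contribute to the conflict.

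**Size if a cohort opened under this text**

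- Participants per cohort: 9 active + 3 placebo = about 12 (Synopsis and Section 9.5).
- Additional cohorts allowed: up to 3 (Synopsis and Section 4.1). How many, if any, would be obesity cohorts is not stated, so one to three is an assumed range.
- Literal eligibility deviations: 12 × 1 = 12 up to 12 × 3 = 36.

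**Evidence of intended scope**

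- Section 4.2.1 states the minimum stable metformin dose as a requirement for participants with T2DM, then says obesity cohorts may be enrolled.
- Section 6.8.1.1 places the metformin requirement on those who enroll with T2DM.
- The notes to criteria 4 and 6 and the exclusion sub-bullet would serve no purpose if people without diabetes could never enter.

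**Status of the text.** The Protocol's document history lists only the version of 21 October 2021. The SAP's version table gives no associated protocol amendment for either SAP version. Neither document shows a correction.

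**The case against.** The strongest reply is that the Protocol, read as a whole, leaves no real doubt. Sections 4.2.1 and 6.8.1.1 limit the metformin requirement to participants with T2DM, Section 4.1 permits obesity cohorts, and three separate statements in Section 5 presuppose them. Only criterion 3 read alone produces an empty set. The obesity cohorts are also optional throughout, and Section 6 of SAP version 2, dated 28 July 2022, still speaks of them conditionally.

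Most of this stands, and it limits the consequence. It does not remove the defect: sites screen against the numbered criteria, and nothing in Section 5 says that criterion 3 gives way to the rationale or to the concomitant-therapy section.

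A reader might go further and infer that the rule in fact blocks the obesity part of the study. The documents do not support that. The no-waiver sentence bars advance approval of deviations; it does not bar amending the criterion, and Appendix 1 (Section 10.1.1) sets out the amendment route. Nor do the documents show that any obesity cohort was opened, so there is no evidence that any deviation occurred.

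**Conclusion.** The point holds as an internal inconsistency that is wrong as written. Criterion 3 and its note apply to everyone, lack the exception given under criteria 4 and 6, and conflict with exclusion criterion 1 for the obesity population.

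The size is conditional. On the literal reading, every participant in an obesity cohort would be an eligibility deviation: about 12 per cohort, or 12 to 36 for one to three cohorts of the stated size. If no such cohort opens, the number is zero.

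A reader might see a questionable design choice here, or a threat to the trial's results. Neither follows. The intended population is clear from Sections 4.1, 4.2.1 and 6.8.1.1, and the planned T2DM cohorts meet criterion 3 as it stands. The sample size was chosen empirically (Section 9.5), no hypothesis is tested (Section 9.1), and the SAP keeps the two populations apart in its placebo groups, demographics and baseline tables (Sections 6, 6.2.1.1 and 6.6.1). No endpoint, analysis set or estimate changes. This is a low-severity correction, worth making because the affected population is named in the primary and secondary objectives.

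**What to change.** Before any obesity cohort opens, reconcile criterion 3 with Sections 4.1, 4.2.1, 5.2 and 6.8.1.1. Add a scope statement in the style of the notes to criteria 4 and 6: criterion 3 and its note apply only to participants who enter the study with T2DM, and not to the non-diabetic obesity population, if enrolled.

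The cost is one line in a protocol amendment and its ethics committee and regulatory handling under Section 10.1.1. The change only states in the operative rule the scope already given in Sections 4.2.1 and 6.8.1.1. Eligibility for the T2DM cohorts, the sample size and the SAP need no change.
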